Aim 1) to examine if patients randomly assigned to a brief overdose prevention intervention report reduced overdose risk behaviors (e.g., higher dose, concurrent alcohol use, concurrent other drug/medication use, returning to normal dose after breaks in use) over one year of follow-up compared to patients assigned to equal attention EUC.

Aim 2) to examine if patients randomly assigned to a brief overdose prevention intervention have lower total quantities of opioids prescribed (from pharmacy fill records) and aberrant opioid use (e.g., using for reasons other than pain, obtaining opioids from someone other than primary provider) over one year of follow-up compared to patients assigned to equal attention EUC.

The study will include two **secondary aims**: **1)** to examine if patients randomly assigned to the brief intervention have fewer non-fatal overdoses and other medication-related adverse events (emergency department visits, over-sedation, injuries), better functioning, and more often store and dispose of opioids safely compared to patients assigned to EUC; and **2)** to examine mediators (motivation and self-efficacy) and moderators (OIF/OEF/OND status, baseline mental health) of intervention effects.

The proposed POST study will increase our understanding of strategies to reduce adverse outcomes related to prescription opioid use, namely, risk of overdose, among VHA primary care patients. This study is the next logical step in addressing the risks of prescription opioid use among VHA patients, providing critical, initial data to inform VHA clinicians to prevent adverse opioid-related outcomes. Knowledge generated from

this pragmatic trial is likely to have broad implications for improving safe opioid use, the enhancement of PC-MHI services, and the quality of pain care for current and future VHA patients.

BACKGROUND

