Patient safety. During the study, we may determine that a participant is at serious, imminent risk for serious self-harm related to their OA use. Study staff will notify the participant's prescriber in this situation and will make additional referrals to mental health or emergency services as needed. These participants will be withdrawn from the study and will not be included in analysis (see section on Feedback to Providers on page 11). For non-OA related risks, such as suicidal ideation, staff will discuss the risks of participation with the patient and review screening responses and the medical chart (e.g., for ongoing mental health care) to decide study eligibility. If any of these determinations are unclear, staff will consult with the supervising psychologist ([name]) or psychiatrist ([name]), both of whom have expertise in assessing suicide risk. Participants who report acute suicidality will be able to continue with study procedures at a later time and will be referred to same-day care through either a PC-MHI-based Psychiatrist or the ED. If treatment needs are not urgent, the participant will be referred to specialty mental health and continue with study protocols. Those participants in the trial who report suicidality at a 3-, 6-, or 12-month follow-up assessment will be connected to the appropriate services (outlined in the Safety Monitoring Plan section on page 21).

Usual care, intervention, and EUC procedures. Both intervention and EUC participants will receive the Long-Term OA informed consent and will review the VHA's "Taking Opioids Responsibly for Your Safety and the Safety of Others" pamphlet with a study therapist (usual care). The study therapists will coordinate with the patients' prescribing physicians to document this process if a participant had not already provided informed consent. For the intervention condition, the informed consent process will lead to a tailored, ME-adherent discussion of reducing the risks of OAs, but for the EUC condition, the informed consent process will be followed by psychoeducation on topics related to pain management, will not be tailored, will not include elements of ME, and will not include content on overdose risk behaviors. If a patient expresses a wish to change their OA regimen after any of the intervention or control content, the study therapist will assist the patient in arranging an appointment with their prescriber.

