Intervention. The intervention session is tailored on knowledge, values, concerns, barriers, and skills/tools for managing pain. It combines elements of ME and cognitive behavioral therapy (CBT) and uses the structure of ME brief interventions. Participants are presented with a variety of risk reduction strategies, including abstinence of all substances except prescribed medications, not combining substances, and taking medications as prescribed. Participants are provided with a number of strategies for coping with pain that may reduce reliance on OAs, such as meditation, activity pacing, stretching, exercise, ice or heat, eliciting support from friends and family, and distraction. The therapist prompts the patient to reflect on which tools are likely to help him/her personally, barriers to using those tools, and plans for overcoming those barriers. The intervention does not recommend that participants stop or reduce their OA use below prescribed levels, but participants who express concern that the benefits of OAs may be outweighed by the harms are guided on how to discuss this concern with their prescriber. The session includes the following organization:

Explore: 1.) Introduce purpose of the session, affirm autonomy to make decisions; 2.) Elicit participants' strengths, values, and goals. 3.) Guide discussion of tailored behavioral history (OA use, other drug and alcohol use, overdose risk behaviors) and pain experiences using open-ended questions/probes.

Guide: 1.) Review role of cognitive factors in pain; 2.) Review risk factors for overdose, with particular emphasis on risk factors for OA overdoses, using an "elicit-provide-elicit" approach;¹⁰ 3.) Review other risks of OA use (oversedation and resulting injuries, impaired driving) and safe storage and disposal; 4.) Guide discussion of potential changes to risk behaviors and use of tools, using menus/lists, eliciting benefits of change, reflective statements, clarifying ambivalence, and anticipating and discussing barriers to change; 5.) Use confidence rulers to elicit importance, confidence, and intention to change.

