Enhanced Usual Care (EUC) condition. In addition to covering the VHA’s long-term OA informed consent process, the control therapist will provide participants educational content with an overview of pain conditions. The overall style will be didactic. This EUC condition will include some information related to risks of OA use as part of the informed consent and will consequently have sufficient face validity as an intervention on OA safety to effectively blind participant to randomization. The VHA pamphlet that is part of usual care lists alternatives to opioid therapy, such as exercise, weight loss, relaxation training, and injections, some of which are also strategies for pain coping. However, the EUC therapist will not use the ME approach of discussing which of these treatments the participant might consider using and strategies for overcoming barriers to their use. Thus, the control condition represents the delivery of standard aspects of VHA care related to OA safety under usual practices and also accounts for potential effects of attention. Therefore, this study will determine if the intervention leads to greater reductions in overdose risk behavior as a result of ME therapeutic style and specific content, rather than due to amount of contact with a clinician.

Feedback to prescribers. We will notify all participants’ prescribers that their patient is at risk for overdose due to their medication regimen and/or OA use behaviors. The notification will include information that we will have discussed this risk with the patient and will occur at the point that intervention or EUC protocols for that patient are completed. This notification will be done for both intervention and control participants to avoid potential differential effects on measurement (because notification to providers could impact future self-report).

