Data collection procedures. Assessments will be self-administered paper-pencil surveys, and research staff will be available to clarify questions. There are five assessments: baseline, post-test, and 3-, 6-, and 12-month follow-up. This assessment schedule will be able to measure if intervention impacts both proximal (e.g., self-efficacy) and distal (e.g., overdose risk behavior) outcomes and to allow enough time to pass to detect less common outcomes (e.g., non-fatal overdose and emergency department visits). All assessments will occur in an area where privacy and confidentiality can be maintained and will take up to 1 hour. When the participant has limited time, the assessment may be completed over the phone. For the post-test, the study therapist will have someone else on the team complete that assessment, or schedule a time for another study member to call back the participant. This will ensure that we are collecting accurate feedback from the participants on the

intervention sessions. This length is comparable to prior research assessments at the Ann Arbor VAMC. Privacy during assessments will be achieved by making sure no one can overhear the conversation. If applicable, research staff will ask others to leave the room during interviews. Baseline assessment will occur at the time of recruitment or shortly after. After intervention or EUC procedures, participants will complete a brief post-test assessment to measure changes in knowledge, self-efficacy, and motivation. Participants will be given \$30 (+\$5 for the urine drug screen [UDS]) for completing the baseline and post-test assessments. Participants will be given an additional \$10 at each assessment to assist with travel expenses.

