
Mediators and process measures. (*Baseline, Post-Test and Follow-up, except where noted*)

Knowledge of Overdose Risk Factors. Knowledge of overdose risk factors (OK) will be assessed with a checklist adapted from prior studies²⁶ with additional items for OA overdose specifically (OEND). In our pilot RCT, 56% of participants misidentified at least one risk factor. In addition, at Baseline and Follow-up, we will assess participant's involvement in overdose education and naloxone distribution.

Motivation and Self-Efficacy. Behavioral intentions (motivation; BI), self-efficacy, and readiness (SEOS) to change will be measured with 6 visual analog rulers.⁹² These constructs are considered critical to ME interventions.¹⁰

Perceived Satisfaction and Utility (Post-test only). A five-point Likert scale (from "really didn't like it" to "liked it a lot") will elicit satisfaction (PSU-I & C).⁹³ We will use similarly-structured questions⁹⁴ to measure the perceived helpfulness of specific intervention components.

Other factors. (*Baseline and Follow-up, except where noted; collected to inform later implementation, to characterize study sample, and/or to examine moderators of effect*)

Suicidality. We will use select modified items (3) from the National Comorbidity Survey (NCS⁹⁵) that will assess past 12 month suicidal ideation and suicide attempts. Follow-up assessments will inquire about the time since last assessment.

Driving after consuming OAs. For our prior work, we adapted items from the National Survey of Drinking and Driving Attitudes and Behaviors⁹⁶ to OA use (included in ORB). Frequency is assessed with a 5 point Likert scale.

Pain Severity and Functioning. We will use select items (7) from the Brief Pain Inventory-Short Form (BPI)⁹⁷ to assess pain interference on a 11-point numeric rating scale (0=Does not interfere, 10=Completely interferes). The Pain, Enjoyment and General Activity scale (PEG)⁹⁸ is a 3-item questionnaire designed to measure chronic pain in a primary care setting. The Centrality of Pain Scale (CPS)⁹⁹ is a 10-item scale used to assess how patients perceive the role of chronic pain in their lives. The CPS has high internal consistency (Cronbach's alpha = .902).

Alcohol and Drug Use Severity. The Addiction Severity Index (ASI)¹⁰⁰ will be modified to allow participants to self-administer the questionnaire. We will use select items (7) from the ASSIST (WHO¹⁰¹) to assess alcohol use and problems.

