Secondary Aim 2 analyses. Hypothesis 4a: The effect of the intervention on overdose risk behaviors and OA use will be mediated by post-intervention self-efficacy and motivation to change. Hypothesis 4b: OIF/OEF/OND status and baseline psychiatric distress will moderate the effect of the intervention on overdose risk behaviors and OA use. Mediators: In further analysis of the GLMs and GLMMs developed for Aims 1 and

2, we will include potential mediators in additional models and examine changes in effect size for the group indicator. Following the recommendations of Preacher and Kelley¹⁰³, we will use a κ^2 statistic to estimate the effect size and conduct significant testing of the mediation. *Moderators*: An interaction effect between each hypothesized moderator and the group indicator (intervention vs. EUC) will be specified in separate GLMs. For longitudinal analysis, we will examine baseline moderator by group interactions in GLMMs.

Additional analyses. We will examine descriptive statistics of the “perceived satisfaction and utility” measure from the post-test for further refinement of the intervention materials for follow-up. Descriptive statistics will also be used to examine differences between those who participated and those who refused participation of select characteristics. The focus group interviews conducted with prescribers will be entered into NVivo 10. [name] and the coordinator will independently read transcripts and use an iterative process to develop a coding scheme. Final codes will be grouped conceptually into meaningful themes and sub-themes. We will also calculate the number needed to treat to prevent one adverse event and amount of therapist time needed to prevent one adverse event.

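### Secondary Aim 2 names only motivation and self-efficacy as mediators; knowledge of overdose risk factors, which the session also targets and the same post-test measures, is left out, so part of a knowledge effect can be credited to them.

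*Combined protocol and SAP*

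**What the plan says.** **Content of the arms.** Under Usual care, intervention, and EUC procedures, part of the content is common: "Both intervention and EUC participants will receive the Long-Term OA informed consent and will review the VHA's" opioid-safety pamphlet. Beyond that, the EUC session "will not be tailored, will not include elements of ME, and will not include content on overdose risk behaviors". The Guide part of the intervention session, by contrast, includes this item: "Review risk factors for overdose, with particular emphasis on risk factors for OA overdoses". The Choose part goes over risk reduction strategies. EUC is not free of risk information: "This EUC condition will include some information related to risks of OA use as part of the informed consent" (Enhanced Usual Care section).

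**Measures.** The section headed Mediators and process measures opens with knowledge: "Knowledge of overdose risk factors (OK) will be assessed with a checklist adapted from prior studies". Data collection procedures describes a "brief post-test assessment to measure changes in knowledge, self-efficacy, and motivation". The measures table puts the knowledge checklist (OK), behavioral intentions (BI) and self-efficacy (SEOS) on the same schedule: baseline, post-intervention and follow-ups.

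**Analysis.** The secondary aim is "to examine mediators (motivation and self-efficacy", together with moderators. Hypothesis 4a states that the effect "will be mediated by post-intervention self-efficacy and motivation to change". The method is to add potential mediators to the Aim 1 and 2 models, look at the change in the group coefficient, and estimate and test the mediation with kappa-squared. No mediation analysis of knowledge is specified. The only other use stated for it is monitoring of contamination.

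**The concern.** One session is meant to move knowledge, motivation and self-efficacy, and all three are read at the same post-test. Patients who learn more may also be more motivated. If knowledge changes behaviour, a model with arm and motivation alone lets motivation stand in for knowledge. Knowledge is then a confounder of the mediator–outcome path that arises after randomisation, so neither randomisation nor baseline adjustment removes it.

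What is at stake is the reading of Hypothesis 4a. The Background argues that behaviour-change methods should do more than education alone, and the mediator analysis is offered as a way to refine theory about brief interventions. A positive result for motivation or self-efficacy could be reported as support for that mechanism when information carried some or all of the effect.

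**Working it through.** **1. The plan's own figures.** The Power analysis section assumes 80% retention, and 450 × 0.80 = 360, or 180 per arm, with two-sided alpha 0.05. For d = 0.30, z = 0.30 × √90 = 2.85 and power is Φ(2.85 − 1.96) = 81%, which reproduces the stated 80%. No figure is given for the mediation analysis, so everything below is illustration on assumed values.

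**2. Set-up.** The arm raises knowledge K by aK and motivation (or self-efficacy) M by aM, in SD units. Their within-arm residuals correlate at ρ. The outcome depends on K alone, with slope b per SD (the sign does not matter), and has within-arm variance 1. The true indirect effect through M is zero. The model is linear.

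**3. Bias when K is left out.** Given arm, the coefficient of M becomes b·ρ instead of 0. The indirect effect through M is then aM·b·ρ and the total effect is aK·b, so the share wrongly credited to M is aM·ρ/aK.

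- aK = aM = 0.5: 0%, 20%, 40%, 60% at ρ = 0, 0.2, 0.4, 0.6.
- aK = 0.5, aM = 0.2: 0%, 8%, 16%, 24%.

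Simulation with 360 patients agreed to within one percentage point. With K in the model, the indirect effect through M was about 0 throughout.

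**4. How often mediation is falsely declared.** The rule used is joint significance of arm→M and M→outcome. For arm→M, power is 81% at aM = 0.3. At aM = 0.5 it is Φ(0.5 × √90 − 1.96) = 99.7%. For M→outcome without K, SE = √[(1 − b²ρ²)/360]. The two are multiplied; aK = 0.5.

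| b | ρ | coefficient bρ | z | M→outcome significant | false mediation (aM 0.3 to 0.5) |
|---|---|---|---|---|---|
| 0.25 | 0.2 | 0.050 | 0.95 | 15.8% | 13–16% |
| 0.25 | 0.3 | 0.075 | 1.43 | 29.7% | 24–30% |
| 0.25 | 0.5 | 0.125 | 2.39 | 66.7% | 54–67% |
| 0.10 | 0.2 | 0.020 | 0.38 | 6.7% | 5–7% |
| 0.10 | 0.3 | 0.030 | 0.57 | 8.8% | 7–9% |
| 0.10 | 0.5 | 0.050 | 0.95 | 15.8% | 13–16% |

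Simulation at b = 0.25 gave 12–15%, 22–27% and 51–66%. With K in the model the rate is 0.05 × 0.81 = 4% to 0.05 × 0.997 = 5% (simulation 3–5%). At ρ = 0 both models sit near 5%, so the excess needs a correlation.

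**5. Overall effect in that scenario.** At aK = 0.5 and b = 0.25 the total effect is 0.5 × 0.25 = 0.125 SD, well below the 0.30 SD the trial is sized for. Power is Φ(0.125 × √90 − 1.96) = Φ(−0.77) = 22%; simulation gave about 20%.

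**6. Cost of adding K.** The standard error of the M path changes by √{(1 − b²)/[(1 − b²ρ²)(1 − ρ²)]}. With b = 0.25 this is √[0.9375/(0.9944 × 0.91)] = 1.02 at ρ = 0.3 and √[0.9375/(0.9844 × 0.75)] = 1.13 at ρ = 0.5. As b approaches 0 it becomes 1/√(1 − ρ²), or 1.05 and 1.15. The range is therefore about 2–15%. With a true M effect of 0.15 SD per SD, simulated power to declare mediation by M fell from about 65% to 60% (ρ = 0.3) and 54% (ρ = 0.5).

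**The case against.** **The protocol tests a package.** The Enhanced Usual Care section attributes any benefit to ME style together with the session's specific content, as against amount of contact. This stands. A reader might infer that the main comparison is confounded by information. It is not: information is part of the treatment, and the randomised estimates for Aims 1 and 2 are unbiased by this.

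**The information gap is partial.** Both arms get the consent and pamphlet, and EUC carries some risk information. This also stands. It would be wrong to read EUC as having no risk content, and a smaller gap means a smaller shift in knowledge. The exclusion of overdose risk behaviours from EUC remains.

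**The plan leaves room for knowledge.** It heads the list of mediator measures, and the method refers to potential mediators without limiting the list. But nothing commits to analysing it, and the plan says hypotheses are set in advance. The two sections need aligning.

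**The numbers are assumed, and the rule is a stand-in.** No path size or correlation comes from the documents, and the plan's theory puts self-efficacy and motivation first. With b = 0.10 the error is near nominal unless ρ is large. The Aim 1 outcome is a count, and the planned test is kappa-squared with change in the group coefficient, so the percentages do not describe that test. The bias in step 3 does not depend on the decision rule, and kappa-squared is built on the same indirect effect.

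**The remedy is incomplete.** Risk information is delivered by an ME technique, and knowledge may itself raise motivation. The joint model therefore cannot fully separate ME from information.

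**Conclusion.** The point holds and is confined to Secondary Aim 2. A measured variable that the session targets is missing from the mediation hypothesis. If it affects the outcome and correlates with motivation or self-efficacy, their indirect effects will be biased. On the assumed values, 0% to about 60% of a pure knowledge effect is credited to the wrong mediator. The false-mediation rate runs from near 5% to about 65% under a joint-significance rule at N = 360. Both ranges depend mainly on the knowledge-to-outcome slope and the residual correlation, neither of which the documents give.

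A reader might go further and infer that the wrong programme would be rolled out. The documents do not support that. The dissemination plan does not make release of the materials depend on the mediation result. In the scenario with the high error rates, only about one trial in five would show a significant overall effect to attribute. What is at risk is the explanation of an effect, not the evidence that one exists.

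**What to change.** In Secondary Aim 2 and Hypothesis 4a:

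- Name the post-test knowledge score (OK) as a parallel mediator, entered together with BI and SEOS.
- Report the specific indirect effect of each mediator, with and without knowledge in the model.
- Interpret a motivation or self-efficacy effect as distinct from knowledge only if it persists in the joint model.
- State that this reduces but does not remove the ambiguity, because mediators are not randomised and knowledge may raise motivation. Only a control arm given the same overdose content didactically would separate the two.

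The cost is wording and one more model. The score is already collected at the right times. The price in precision is the 2–15% wider standard error shown above and a modest loss of power for a true motivation effect.

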Staff will approach selected patients in the waiting area or after their appointment ends and will describe the study briefly. Additionally, the patients' documents for the visit will indicate their eligibility so that their provider can remind them that they may be approached about participating in a research study, consistent with IRB-approved processes in ongoing studies at the study site. Staff will escort interested participants to an area where privacy and confidentiality can be maintained to conduct informed consent for the study and additional screening procedures. Privacy during assessments will be achieved by making sure no one can overhear the conversation. If applicable, research staff will ask others to leave the room during interviews. Participants who are not able to stay after their medical appointment will be asked to schedule an appointment with study staff to complete enrollment. Additional screening questions will determine: 1) whether the potential participant has stopped using OAs, 2) whether the potential participant will reduce their OA dose to ≤ 20 MEM/day in the next

6 months, 3) cognitive impairment, and 4) any other exclusion criteria not noted from the medical record. Participants will be given the option to complete their baseline assessment and receive the intervention or EUC protocols at that time, or will complete it within 5-10 days (in-person or over the phone). Participants with limited time will be given the option to complete the informed consent process in-person, then follow-up with a phone call to complete the survey assessment and intervention. This will be used as a last resort for those participants who have restricted availability or concerns with travel. Participants who chose this option will be able to complete the urine drug screen in-person after completing the informed consent document. They will be provided with the handouts for the session at the time of the in-person informed consent process. Minimal de-identified data (e.g., gender, race, age, reason for refusal) will be collected on eligible patients who are not recruited or refuse to participate in the study to better understand how they differ from those that do participate on key factors and reasons for refusing participation so the study can understand potential bias in sample frame.

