Randomization. Participants will be individually randomized to receive either the intervention or EUC after completing the baseline. The coordinator will supervise the randomization, which will be conducted by the analyst, using computerized block-randomization stratified by OEF/OIF/OND status in blocks of 10.

Intervention and EUC condition delivery procedures. The intervention and EUC procedures will each take approximately 30 minutes to complete, in addition to the chronic OA therapy informed consent. These sessions will take place in a private room or over the phone in a private office to ensure privacy and confidentiality. Consistent with our prior interventions, the sessions will be computer-aided to enhance fidelity. For the intervention, the therapist uses the computer aid to progress through a series of prompts, which ensures that each step of the intervention is covered and reminds therapists of specific ME tools relevant to each step. The computer aid also includes screens with suggested options/choices that can be shared with participants who have trouble generating goals, values, strengths, and tools without prompting. The EUC condition will also use a computer aid that will include a series of prompts and non-interactive visual aids related to the content of that condition. Feedback to the participants' prescribers will be given based on the protocol developed through the process described above.

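### On the phone route the session handouts are given at consent, before baseline and randomization, so baseline knowledge, intentions and self-efficacy can be measured after exposure, and EUC is exposed too if the handouts carry intervention content

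*Combined protocol and SAP*

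**What the plan says.** All sections cited are in the combined protocol and SAP, under Research Design and Methods unless noted.

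- **Recruitment and screening procedures.** Participants with limited time may consent in person, "then follow-up with a phone call to complete the survey assessment and intervention". Of the same participants it says: "They will be provided with the handouts for the session at the time of the in-person informed consent process". On frequency it says only: "This will be used as a last resort for those participants who have restricted availability or concerns with travel". A deferred baseline and session are to be completed within 5-10 days.
- **Randomization.** "Participants will be individually randomized to receive either the intervention or EUC after completing the baseline".
- **Usual care, intervention, and EUC procedures.** The EUC session "will not include elements of ME, and will not include content on overdose risk behaviors". Both arms review the same VHA opioid-safety pamphlet with a study therapist.
- **Risk of contamination.** EUC contamination is recognized as a category. The controls are therapist adherence to the manual, review of EUC sessions, and assessment of change in self-efficacy, motivation and knowledge in all participants. Handouts are not mentioned.
- **Data collection procedures; Measures.** Knowledge (OK), intentions (BI) and self-efficacy (SEOS) are taken at baseline, at post-test and at follow-up. The post-test exists to measure change in these constructs.
- **Human Subjects, Sources of Materials.** The phone route is described again, without the sentence on handouts.

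**The concern.** The handout sentence is an explicit timing rule, and it sits badly with the section that follows it. When the handouts change hands the participant has no baseline survey on file and no arm. Two things are at stake.

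First, OK, BI and SEOS are the measures most easily moved by reading about opioid safety or coping with pain. A baseline taken after the participant has had such material at home for some days is no longer a clean starting value.

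Second, the trial contrasts a tailored motivational session that covers overdose risk with an EUC session that leaves overdose risk behaviors out. If the handouts reflect the intervention session, EUC participants on this route could take that content home. The planned safeguards are aimed at what therapists say and would not see it.

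**Working it through.** **Order of events on the phone route, from the two sections read together**

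1. In-person consent; session handouts given (Recruitment and screening procedures).
2. Baseline survey, later, by phone (same section).
3. Randomization, once baseline is complete (Randomization).
4. Intervention or EUC session by phone, then post-test.

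Step 1 precedes steps 2 and 3, so the handouts can be neither matched to the arm nor withheld until baseline.

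**What staff can hand over at step 1**

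| Material given | EUC exposed to intervention content? | Baseline OK, BI, SEOS after exposure? |
|---|---|---|
| Common VHA pamphlet only | No | Yes |
| Both arms' handouts | Yes, if the intervention set carries such content | Yes |
| Intervention handouts to everyone | Yes, if they carry such content | Yes |

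The baseline problem appears in every row, provided the material bears on opioid safety or pain coping and is read. The contamination problem depends on content that the protocol does not describe.

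**Can the planned checks detect it?** Session review hears what the therapist says, not what the participant has read at home. The change check compares later values with baseline; if an EUC participant reads the material before baseline, baseline is already raised and the measured change is smaller. That check is therefore blunted where it is needed.

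**Size.** The plan's power figures reproduce, within 2 points, from its own inputs (Power analysis: 180 per arm, two-sided alpha 0.05).

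- Count outcome: means 1.9 and 1.9 × 0.80 = 1.52. SE of the log rate ratio = √(1/(180 × 1.9) + 1/(180 × 1.52)) = 0.0811. |ln 0.80| = 0.2231. Power = Φ(0.2231/0.0811 − 1.96) = 78.6%, against 80% stated.
- Continuous outcome: Φ(0.30/√(2/180) − 1.96) = 81.2%, against 80% stated.

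Let f be the share of EUC on the phone route and c the share of the full effect that handouts alone would carry. Neither is in the documents; both are assumptions. The EUC mean becomes 1.9 × (1 − 0.20·f·c), and d becomes 0.30 × (1 − f·c).

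| Assumed f·c | Example | IRR | Power, count | d | Power, continuous |
|---|---|---|---|---|---|
| 0 | common pamphlet only | 0.800 | 78.6% | 0.300 | 81.2% |
| 0.025 | f = 5%, c = 50% | 0.804 | 76.6% | 0.2925 | 79.2% |
| 0.05 | f = 10%, c = 50% | 0.808 | 74.6% | 0.285 | 77.1% |
| 0.10 | f = 20%, c = 50% | 0.816 | 70.2% | 0.270 | 72.6% |

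The table shows how power would respond to dilution. It does not estimate what this plan loses.

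**The case against.** The best defense starts from the content of the handouts. The only printed session material the protocol names is the VHA pamphlet, which both arms review anyway; the arm-specific content it describes is a therapist-led discussion with computer-aid screens. If the handouts are that pamphlet, both sections can be followed with no contamination. This stands, and it is why contamination is conditional here.

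A reader might go further in four ways that the documents do not support.

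- *That allocation concealment is broken.* This would require the arm to be settled at consent, which the Randomization section rules out.
- *That the baseline shift biases the comparison between arms.* Material given before randomization cannot depend on the arm, so any shift in OK, BI or SEOS is balanced in expectation. It affects within-person change.
- *That the mediation analysis is distorted.* Hypothesis 4a uses post-intervention self-efficacy and motivation and states no change-from-baseline model.
- *That a particular loss of power follows.* This needs values for f and c that the plan does not give. Crediting paper read alone with half the effect of a tailored 30-minute session is generous, and the route is meant as a last resort.

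It is also fair to say that behavioral items are little exposed, because baseline generally asks about the past year or lifetime, and that the contamination section does recognize the general category. None of this changes the order of events, or the fact that even the common pamphlet would precede the baseline knowledge and self-efficacy items.

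**Conclusion.** The concern holds in a limited form. As written, phone-route participants receive session material before the baseline survey and before randomization. Baseline OK, BI and SEOS can therefore be taken after exposure, which would shrink measured pre/post change in both arms. That rests only on the participant reading the material and on its bearing on those constructs.

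EUC contamination is possible and not established. It requires that the handouts carry intervention content. If they do, the bias is toward no difference and the planned session reviews would miss it. No power loss can be attributed to the plan: it is zero with common material only, and otherwise depends on two unknown quantities. The motivational discussion itself still follows randomization in every case. The timing rule should be changed because the change is small and removes both possibilities.

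**What to change.** In Recruitment and screening procedures, replace the handout sentence with wording to this effect:

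> For participants using the phone option, anything handed over at consent is limited to material that both arms receive and is sealed until the baseline survey has been completed. Any arm-specific handout is mailed or sent electronically only after the baseline survey is complete and the participant has been randomized.

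State what the handouts contain, carry the same rule into Human Subjects (Sources of Materials), and list this route under Risk of contamination.

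Record use of the phone option at consent, and plan a sensitivity analysis of the main contrasts and of OK, BI and SEOS change without these participants. Because the route is chosen before the arm is known, leaving them out of both arms keeps the comparison randomized.

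**Cost.** A short text change and some postage. Where arm-specific handouts are needed, the single call may become two contacts, with a short delay and a small risk that some randomized participants miss the session. Using common material only avoids this. The seal depends on the participant's cooperation, so staff should ask at the start of the survey call whether it has been opened and record the answer.
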